#### Intervention group: i-CARE

Participants in the intervention group will receive a 12-week i-CARE intervention, which will be designed to cover the core elements of CAD self-care: self-care maintenance, self-care monitoring and self-care management. The intervention will comprise: 1) a single individualized face-to-face session and 2) an internet-based intervention through a mobile application, which is developed by the investigation team of this project. Various behavior change techniques will be used to increase the self-efficacy of CAD patients in enacting self-care behaviors. The details of these two care components are described as follow.

##### 1) Face-to-face orientation session

This single face-to-face session serves to orientate and prepare participants to actively engage in the upcoming internet-based intervention. The research nurse (RA1) will highlight the crucial role of patients themselves in managing the disease by assisting them to understand the links between their self-care behaviors and health consequences. A subsequent interactive skill-building session to ensure patients acquire the skills required for performing self-monitoring techniques, including blood pressure, heart rate and blood glucose measurement. The participants will be required to perform return demonstration to ensure skill acquisition. The nurse will then introduce the mobile application and assist the participants to register an account. Upon successful registration, a password will be provided. He/she will demonstrate the key functions of the application and assist the participant to personalize the setting according to their individualized risk profile and preferences. The nurse will emphasize the importance of compliance to self-care behaviors and will facilitate the participants to set self-directed goals at the end of this session.

##### 2) Internet-based intervention via a mobile application

The mobile application will consist of three key user interfaces, including the self-monitoring dashboard, the interactive self-care modules and the chat room. A group of 12 CAD patients with diverse socio-demographic background will be invited to test the user interface. Their comments will be incorporated to optimize the design, content, layout and visual features before the application is formally launched for testing.

The self-monitoring dashboard is a personalized interface that allows participants to select relevant parameters for regular self-monitoring according to their own risk profile, which include blood pressure, heart rate, lipid profile and blood glucose. In addition, the physical activity levels of each participants will be monitored with a pedometer. The

number of steps will be synchronized to the dashboard regularly. All parameters will be self-measured and entered to the dashboard by the patients on a daily or weekly basis except lipid profile, which will be entered by the research nurse according to the results extracted from the Clinical Management System. The participants can customize the application features on receiving notifications and motivational messages. The input data will be presented in a graphical format to visually demonstrate the changes over time.

The interactive self-care modules will cover the following topics: 1) CAD, its symptom monitoring and management, 2) medication management, 3) personalized risk factor control (e.g. body weight reduction, smoking cessation, blood pressure control, glycemic control, lipid control, and insomnia), 4) healthy diet, 5) activity and exercise, and 6) stress management. The contents of this module are consistent with the recommendations of major international guidelines on CAD management. A variety of interactive features will be used to improve engagement, motivation and knowledge acquisition of the participants, including the use of audio-visual format with animations and illustrations, peers with successful self-care experience will also be invited to share the tips with the participants. The participants will be guided to establish an individualized action plan, which an exhaustive list of actions in categories will be presented for the participants to select those actions according to relevancy and preferences.

The chat room will serve as a platform to facilitate the nurse to provide coaching to motivate and facilitate behavioral changes of the participants. The nurse will review the self-monitoring data and keep track on the progress of goal attainment of each participant. He/she will initiate chatting with the participants in this platform weekly, to identify any problems that the participants encountered in their daily practice of self-care behaviors, and will explore the underlying barriers, then advise resolving methods to minimize the barriers and improve adherence. Health counselling and advice given will be documented to guide subsequent communication. Throughout the process, the nurse will adopt therapeutic communication skills, and a supportive and non-judgmental attitude. The participants can also initiate the communication with the nurse in the chat room regarding disease management. The nurse will offer advice and counselling accordingly during office hours. An automatic system-generated message will pop up to remind the participants to seek urgent medical care for newly onset symptoms that may suggestive of disease exacerbation or deterioration.

#### Control group: Usual care

The control group will continue to receive conventional care as arranged by the hospital. They will not receive any structured cardiac rehabilitation interventions during the study period.

#### Fidelity monitoring of the study intervention

To optimize fidelity of the study intervention, a training manual will be used to guide the intervention delivery. The research nurse (RA1) will receive two weeks of comprehensive training from the investigation team on CAD, principles and skills in patient education, methods to deliver the study protocol and counselling via the chatroom. For fidelity monitoring, the principal investigator will randomly select 10% of the face-to-face educative sessions for fidelity monitoring. The educative sessions will be audiotaped with the participants' consent, the chat record between the research nurse and participants in the chatroom will be reviewed. Thirdly, the login activities, number of completed sessions, the self-monitoring dashboard activities of all participants will be tracked. All of these data will be used to interpret the RCT findings.

## **Outcome measures**

### *Primary outcome*

#### Self-care behaviors:

The Chinese version of Self-Care of Coronary Heart Disease Inventory (SC-CHDI) will be used to measure self-care behaviors. This self-reported SC-CHDI (22 items) measures self-care maintenance, self-care management and self-care confidence on a four-point response scale. Each subscale score is transformed to 100 points, with higher scores indicate better self-care for that attribute. It has acceptable reliability (Cronbach's alpha: 0.76 – 0.87), good factorial and convergent validity.

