The priority of care for CAD is to delay the progression of coronary arterial occlusion and improve prognosis through pharmacological and non-pharmacological means to control the modifiable risk factors, including lifestyle behaviours. Viewing the chronic nature of CAD, it requires patients to practice persistent self-care in a long-term manner for successful disease management. Self-care is defined as the ability of individuals to engage in the decision-making process for the purpose of maintaining health and managing his/her chronic health conditions. Effective self-care has been consistently identified in empirical studies as the most cost-effective means of achieving disease management goal and is considered fundamental to the prevention and management of chronic diseases. The concept of self-care of chronic illness comprises three core elements: self-care maintenance, self-care monitoring and self-care management. Self-care maintenance requires adherence to behavioral modifications to maintain physical and emotional stability, whereas self-care monitoring and self-care management refer to self-observation of signs and symptoms and response to the observed signs and symptoms respectively. In the context of CAD, self-care actions including lifestyle modifications such as maintenance of a healthy diet and physical activity, medication adherence, control of risk factors such as blood glucose for diabetes and blood pressure for

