### Study participants

Adults will be eligible to join the study if they are: 1) living in the community, 2) owning a smartphone with internet access, 3) communicable in Cantonese, 4) able to type in Chinese or English, and 5) with a confirmed diagnosis of CAD. Individuals will be excluded if they have: 1) enrolled to a structured center-based or home-based cardiac rehabilitation programme in the past year, 2) known psychiatric problems, 3) impaired cognitive functioning (i.e. Abbreviated Mental Test  $\leq 6$ ), and 4) terminal disease with life expectancy  $< 1$  year.

For the RCT, the sample size is determined on the basis of a systematic review that identified small to medium effect sizes (0.42–0.66) of information and communication technology-based cardiac rehabilitation on health behaviors among patients with CAD. This study will conservatively assume an effect size as 0.4. The power analysis software PASS 14 (NCSS, Kaysville, UT) estimated that a sample size of 100 subjects per study group would give the proposed two-arm randomized controlled trial 80% power at a two-sided 5% level of significance to detect an effect size of 0.4 on the primary outcome between the control and intervention groups at the post-intervention time point. After allowing for a potential dropout rate of up to 25%, 268 subjects (i.e. 134/group). For the qualitative phase, a criterion sampling of 30 participants who have received the i-CARE program will be invited to join on the basis of their post-intervention changes in the primary outcome, with 10 participants from each

category (low, medium and high percentile). Maximum variations in the participants' sociodemographic and clinical characteristics will also be considered in the sampling procedure to ensure a wider range of data.

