#### Disease-specific health-related quality of life (HRQoL):

The Chinese version of MacNew will be used to measure disease-specific HRQoL. It consists of 27 items measuring HRQoL in three domains (physical, emotional and social). Each item is rated on a 1-7 scale, and a global score is calculated by summing the item scores, a higher score represents better HRQoL. MacNew has been validated in Hong Kong Chinese, which indicated satisfactory internal consistency (Cronbach's alphas  $\geq 0.87$ ) and test-retest reliability, concurrent and discriminant validity.

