## **Data collection procedure**

After obtaining the approval from the respective ethics research committees, the research nurse will recruit eligible participants from the cardiac clinics and wards of two regional hospitals in Hong Kong. The local PI will identify potential subjects from the admission record and follow-up list of the cardiac ward and clinics respectively, and refer them to the research nurse. The research nurse will screen their eligibility according to the predefined criteria. All the eligible patients will be invited to participate. He/she will introduce the study to potential participants verbally, supplemented with a written information sheet. After obtaining the participants'

written informed consent, the nurse will collect socio-demographic and clinical data through patient's self-report and medical record review, while the nurse will assist participants to complete the SC-CHDI, SAQ and MacNew through a secured online platform Qualtrics. The physiological, anthropometric and biomarkers will be collected according to the standard protocol. The research nurse will then allocate the participants into intervention or control group by block randomization, to receive the i-CARE intervention or usual care, respectively. The post-intervention data will be collected through the mobile application, a message will be popped up to remind the participants at 3 and 6 months thereafter. A trained research assistant who has no knowledge of the group allocation, will be responsible for collecting the post-intervention physiological, anthropometric and biomarkers. A subsample of the participants will be invited to participate in the qualitative phase. Semi-structured interviews will be conducted by the principal investigator with an interview guide, which includes open-ended questions to enquire about their engagement experience in the intervention.

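### The primary outcome is three separately scored SC-CHDI subscales with no lead score or multiplicity rule, but the sample size covers one 5% test; if any subscale can support the claim, two-sided error is about 11–14% (assumed correlation 0.7 to 0)

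*Combined protocol and SAP*

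**What the plan says.** Self-care behaviors is the only primary outcome. The Outcome measures section says that the SC-CHDI "measures self-care maintenance, self-care management and self-care confidence on a four-point response scale. Each subscale score is transformed to 100 points", with a higher score meaning better self-care on that attribute. It names no total score, lead subscale, visit or success rule. For the MacNew, by contrast, the plan says that "a global score is calculated by summing the item scores".

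The sample size paragraph (Study participants) treats the primary outcome as one quantity. It takes 100 per arm at 80% power and a two-sided 5% level "to detect an effect size of 0.4 on the primary outcome between the control and intervention groups at the post-intervention time point". The qualitative sampling in the same section selects ten participants each from low, medium and high groups "on the basis of their post-intervention changes in the primary outcome".

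Data Analysis applies a GEE to the outcomes over T0, T1 and T2 and calls any two-sided p below 0.05 significant. It names no primary score, no primary contrast and no adjustment for multiple tests.

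The month of the powered visit is also not stated. The intervention section says "Participants in the intervention group will receive a 12-week i-CARE intervention", which points to 3 months, but Data collection procedure says "post-intervention data will be collected through the mobile application, a message will be popped up to remind the participants at 3 and 6 months", so post-intervention covers both visits.

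**The concern.** A sample size for one test at 5% implies one score, one visit and one decision. The outcome section supplies three scores, and the analysis section tests each of them in the same way. Three readings are open:

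- **One score decides.** The planned error and power hold, but the score is unnamed and could be picked once results are known.
- **Any subscale suffices.** The 5% error does not hold.
- **All three must succeed.** Error is controlled, but power is below 80%.

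The background does not settle which score leads. It states: "The concept of self-care of chronic illness comprises three core elements: self-care maintenance, self-care monitoring and self-care management". The intervention is likewise built to "cover the core elements of CAD self-care: self-care maintenance, self-care monitoring and self-care management". The instrument's third subscale is confidence, not monitoring, so the list of self-care elements does not map onto the list of scores.

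The qualitative sampling is affected too. Participants cannot be sorted by change in the primary outcome until it is a single number.

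**Working it through.** **Inputs.** From the sample size paragraph: effect size d = 0.4, two-sided alpha 0.05, power 80%, 100 per arm, dropout 25%. From the outcome section: three subscales. The documents give no correlation between subscales, so a common correlation r is assumed and varied. All figures are for one visit.

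**1. The plan's own figure.** For a two-sample t-test the noncentrality is d·√(n/2). Power is 0.7997 at n = 99 and 0.804 at n = 100, so 100 per arm is right. 100/0.75 = 133.3, rounded up to 134 per arm, 268 in total. The plan's figure reproduces as one 5% test with no split of alpha.

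**2. Any of three subscales, no true effect.** With r = 0, the probability of at least one significant result is 1 − 0.95³ = 0.1426. For r > 0, write each statistic as √r·U + √(1−r)·Eᵢ, with U and Eᵢ independent standard normal, and integrate over U the probability that all three stay within ±1.96. The error is one minus that integral. The benefit-only column counts only results favouring i-CARE; a single test gives 2.5% there.

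| r | Any significant, two-sided | Benefit direction only |
|---|---|---|
| 0 | 14.3% | 7.3% |
| 0.5 | 12.5% | 6.3% |
| 0.7 | 10.9% | 5.5% |
| 0.8 | 9.8% | 4.9% |
| 0.9 | 8.4% | 4.2% |

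**3. Only two subscales count** (confidence read as a mechanism). With r = 0: 1 − 0.95² = 9.75%. With r = 0.7: 8.35%. In the benefit direction: 4.9% and 4.2%.

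**4. All three must be significant, d = 0.4 on each.** The noncentrality is 0.4 × √50 = 2.83. Power is 52.6% (r = 0), 62.3% (0.5), 66.9% (0.7) and 73% (0.9).

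**5. Three subscales kept, error controlled.** 0.05/3 = 0.0167. At 100 per arm:

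- Power for one given subscale tested at 0.0167 is 66%.
- With Holm and d = 0.4 on all three, power for a given subscale is 76% (r = 0) to 74% (0.7), by simulation.
- With Holm and d = 0.4 on all three, power for at least one rejection is 96% (r = 0), 88% (0.5), 83% (0.7), 80% (0.8) and 76% (0.9).
- If only one subscale has the effect, power for at least one rejection is about 68%.
- For 80% on a given subscale at 0.0167, 133 per arm must be analysed. 133/0.75 = 177.3, rounded up to 178 per arm, 356 in total.

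**6. One named score at one visit.** Let ρ be the correlation between baseline and follow-up, with equal SDs and d in follow-up SD units. Baseline adjustment gives an effective effect size of d/√(1−ρ²). A change score gives d/√(2(1−ρ)).

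| ρ | Baseline-adjusted | Change score |
|---|---|---|
| 0 | 80.4% | 51.2% |
| 0.3 | 83.9% | 66.2% |
| 0.5 | 90.1% | 80.4% |
| 0.7 | 97.6% | 95.3% |

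**The case against.** The strongest reply is that a single score was probably intended. The plan lists one primary outcome, uses the singular in the power statement and in the qualitative sampling, and the subscale sentence may only describe how the instrument is scored. On that reading the error is 5% and the power 80%. The Seattle Angina Questionnaire is also described by subscales with no summary score, so the MacNew contrast proves little. The 14% end needs uncorrelated subscales of one questionnaire, and the two-sided figure counts significant harm as a success. The background and intervention sections also treat self-efficacy as a driver of behavior, which would leave two subscales as outcomes.

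Much of this is fair. The inflation is conditional, and the lower figures are shown above for that reason. The visit is most naturally 3 months, and no error figure here uses the choice of visit. The mismatch between monitoring and confidence does not itself affect error. But if one score was intended, the plan still does not say which, and no correlation tried brings the any-subscale error down to 5%.

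Three points about the remedy also stand. Moving to a model with T1 and T2 as the only outcomes is a change of model, and it would omit anyone with neither visit. The 80% requires d = 0.4 on the chosen score; at d = 0.35, 100 per arm gives 69%. And the plan's selection of covariates by baseline p < 0.25 would leave the new primary test not fully fixed unless the covariates are stated.

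**Conclusion.** The concern holds. As written, the plan gives three unadjusted primary scores and no decision rule, and the stated 5% error and 80% power hold together only under a choice that the documents do not make.

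If any of the three subscales can support the claim at one visit, two-sided error is about 11–14% (r from 0.7 to 0), falling to 8.4% at r = 0.9. False claims of benefit alone run at 5.5–7.3% over r from 0.7 to 0, against 2.5%. With two subscales the two-sided error is about 8–10%. If all three must succeed, power is 53–67% over r from 0 to 0.7.

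These sizes rest on assumed equal correlations, normal test statistics and, for power, the plan's own d = 0.4 on each subscale. The missing rule depends on none of these. It must be fixed, because it determines what a positive trial means.

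**What to change.** Before unblinded data are seen, name one SC-CHDI score (for example self-care maintenance) and one visit (for example T1 = 3 months, the end of the 12-week intervention) as the primary endpoint, in both the Outcome measures and Data Analysis sections. Test the between-group difference in that score at that visit, adjusted for its baseline value, at two-sided 0.05. State at the same time which other covariates, if any, enter this test. The contrast can come from a GEE with T1 and T2 as outcomes and baseline as a covariate; that form is optional. Make the other subscales and the other visit secondary, and use the same score and visit for the qualitative sampling.

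**Cost.** Protocol and SAP wording, including the model statement if that GEE form is used, and no extra participants. At the plan's d = 0.4, 100 per arm, 268 in total and at least 80% power stand. An unadjusted change-from-baseline contrast keeps 80% only if the baseline–follow-up correlation is about 0.5 or more. The price is that significance on another score or visit no longer counts as primary success.

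**Alternative.** Keep all three subscales primary, with Holm at the one named visit, and state the power in step 5. An any-subscale claim then needs no extra participants if d = 0.4 on all three and r is no more than about 0.8. Only a requirement of 80% for a given subscale at 0.0167 would raise the total, from 268 to 356. The qualitative sampling would still need one named score.

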### *Secondary outcomes*

#### Functional status:

The Chinese version of Seattle Angina Questionnaire will be used to measure functional status. This 19-item questionnaire consists of five subscales, including physical limitation, angina stability, angina frequency, treatment satisfaction and the disease perception. The respondents have to rate on a 1 to 5 or 6 sequentially coded status. The subscale scores are transformed to a scale of 0 to 100, with higher scores indicate higher level of functioning/ satisfaction and fewer limitations. The Chinese version has been shown to be reliable, valid and sensitive to clinical change.

#### Disease-specific health-related quality of life (HRQoL):

The Chinese version of MacNew will be used to measure disease-specific HRQoL. It consists of 27 items measuring HRQoL in three domains (physical, emotional and social). Each item is rated on a 1-7 scale, and a global score is calculated by summing the item scores, a higher score represents better HRQoL. MacNew has been validated in Hong Kong Chinese, which indicated satisfactory internal consistency (Cronbach's alphas  $\geq 0.87$ ) and test-retest reliability, concurrent and discriminant validity.

#### Physiological and biomarkers:

Physiological parameter (blood pressure), anthropometric measure (waist-to-height ratio) and biomarkers (lipid profile: total cholesterol, high-density lipoprotein cholesterol, low-density lipoprotein cholesterol and triglycerides) will be assessed/collected/tested according to standard protocol. The fasting lipid profile will be measured by a validated point-of-care machine. A capillary blood sample will be collected from a finger stick after 8 hours of fasting. Point-of-care testing has proved reliable and correlates well with the standard laboratory testing.

